POWER ANALYSIS REPORT

Statistical power analysis was applied to decide how many observations to work with for the article study on “**An Evaluation of the Effect of Grain-Like Products on Postprandial Glucose, Insulin and Subjective Saturation Response in Healthy Individuals**”. For power analysis, power values for different sample numbers were calculated with G*Power software. While calculating the power values, the results were determined within the scope of 95% confidence level ($p < 0.05$). Parallel to the research to be carried out, starting from the reference study (Vuksan et al., 2017), the independent samples t-test result applied to describe the mean difference in waist circumference was taken as a basis. The effect size value obtained for the power analysis within the scope of the applied test was calculated as approximately $d = 3.429$. According to the power values, in this study, if a total of 6 observations are studied, a test power of approximately 87.4% is reached. Since the power value we calculated is over 80%, it is statistically sufficient. Figure 1 shows the graph of power values according to the number of samples. In addition, the screen output of the G*Power program is given in Figure 2.

[figure not shown]

Figure 1: Power values for different sample numbers

Analysis:	Post hoc: Compute achieved power
Input:	Tail(s) = Two
	Effect size $d = 3.428571$
	α err prob = 0.05
	Sample size group 1 = 3
	Sample size group 2 = 3
Output:	Noncentrality parameter $\delta = 4.1991247$
	Critical $t = 2.7764451$
	Df = 4
	Power (1- β err prob) = 0.8741037

Figure 2: G*Power screen output

Reference

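### Does a power figure for one two-group test at 5% fall short because the study title names several products and three outcomes?

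*SAP*

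**What the plan says.** The SAP consists of one power analysis report. Its text says that power was computed in G*Power and that "the results were determined within the scope of 95% confidence level". For the test, "the independent samples t-test result applied to describe the mean difference in waist circumference was taken as a basis". The software output in Figure 2 shows a two-sided test with "α err prob = 0.05", "Sample size group 1 = 3" and "Sample size group 2 = 3", an effect size d of 3.428571, 4 degrees of freedom and power 0.8741037. The report concludes: "Since the power value we calculated is over 80%, it is statistically sufficient".

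The outcomes of the study appear only in its title, as the "Effect of Grain-Like Products on Postprandial Glucose, Insulin and Subjective Saturation Response". The report gives no number of products, no ranking of outcomes, no list of hypotheses, no success criterion and no rule for multiple tests.

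**The concern.** The calculation spends the whole 5% on one comparison of two groups, while the title lists three responses and more than one product. If each response were tested at 5% and any one significant result were claimed as a positive finding, the chance of at least one false claim would exceed 5%. If the 5% were instead divided over three tests, each would have less power than the 80% that the report itself sets as its bar. If a control and two products shared the 6 observations, each group would have 2 observations instead of 3. On that reading, the statement that the power is sufficient would not cover the claims the study goes on to make.

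**Working it through.** **Inputs.** From Figure 2 of the SAP: d = 3.428571, n = 3 per group, two-sided alpha 0.05. From the text: the 80% bar. From the title: three responses. The number of products is not given.

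**The report's own figure.** With noncentral t, df = 2n − 2 = 4 and noncentrality = d·√(n/2) = 3.428571 × √1.5 = 4.1991. The critical t is 2.7764 and the power 0.8741. The report's figure reproduces exactly.

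**The adverse scenarios.** The arithmetic is right in each; the assumption is what matters.

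| Scenario | Assumption needed | Result |
|---|---|---|
| Three outcomes, each at 0.05, any one counts | all confirmatory, independent | error 1 − 0.95³ = 14.3% |
| Same, correlated outcomes (simulated) | correlation 0.5 / 0.8 / 0.95 | 13.2% / 11.0% / 8.1% |
| Bonferroni over two tests, alpha 0.025 | two confirmatory tests | 72.8% power per test |
| Bonferroni over three tests, alpha 0.0167 | three confirmatory tests | 62.4% power per test |
| All three must succeed, each at 0.05 | independent | 0.8741³ = 66.8% (at most 87.4% under any correlation) |
| 6 observations over three groups of 2 | three arms | 46.4% per pair (63.5% with pooled df = 3) |

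**Does the report supply these assumptions?**

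- *Each outcome tested at 5%.* The sentence containing "the results were determined within the scope of 95% confidence level" is about the calculation of the power values. It matches "α err prob = 0.05" in the software output. It records an input and sets no testing rule for the trial's outcomes.
- *Three outcomes of equal standing.* The only source is the title. A list in a title gives no outcome confirmatory status.
- *Three arms.* The only layout stated is two groups of 3. The 46.4% and 63.5% belong to a design that the report does not describe.

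**Is there a choice only between excess error and low power?** No. With one primary comparison at 0.05, error is 5% and power 87.4%. With a fixed order, the first test is also run at 0.05 and keeps 87.4%, and the later tests are reached only after success, so 5% holds over the set.

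**Like with like.** The 14.3% is the chance of *at least one* false positive; the 62.4% is the power of *each single* test. The power that matches the 14.3% is the chance of at least one true positive under Bonferroni. If the three outcomes are independent and all have the report's d, it is 1 − (1 − 0.6236)³ = 94.7%. Simulation with correlated outcomes gives about 89% at correlation 0.5, 80% at 0.8 and 71% at 0.95. So even if any one of three outcomes may carry the claim, holding 5% takes power below 80% only when the outcomes are very highly correlated.

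**Holm.** The 62.4% is not the power under Holm. With all three effects at the report's d, simulated Holm power per test is about 79% if independent, 77% at correlation 0.5 and 70% at 0.95.

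**The case for a change.** The strongest case is that this does not depend on a missing multiplicity section. A power figure has meaning only for a specified test, and the report calls its figure sufficient without saying which of the three responses, or which product contrast, it covers. The only variable it names is waist circumference, which is not among the three. The margin over 80% is also thin: at 3 per group, power falls below 80% once two-sided alpha is under about 0.034, so even an equal split over two tests fails. If all three outcomes did prove to be confirmatory with no adjustment, the error rate would exceed 5% at every correlation examined.

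These facts stand. The report does not name its comparison, and the conditional figures are right. They do not show an error in what is written. The sentence that ends in "Since the power value we calculated is over 80%, it is statistically sufficient" rests on the power value of the test that was calculated, and that value is above 80%. Which outcome is primary, and how the others are handled, is commonly settled in the protocol, so silence here does not show that all three are tested for confirmation.

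The waist-circumference source of the effect size is a different matter. It bears on whether d = 3.428571 is credible for this study at all, and every figure above inherits it. Attaching the 87.4% to postprandial glucose in order to resolve the multiplicity question would give that outcome a power that the report does not support.

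**Conclusion.** The concern does not hold. The report calculates one test correctly at the level it states, and it contains no multiplicity rule that could be wrong. A 14.3% error rate or a fall to 62.4% power requires three confirmatory outcomes, and the 46.4% requires three arms; the report states neither. One primary comparison or a fixed order keeps 5% error and 87.4% power for the first test. What remains is that the report does not name the comparison or the standing of the other outcomes, a detail commonly left to the protocol.

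This conclusion assumes only that the unseen protocol may rank the outcomes. If the protocol made all three confirmatory without adjustment, the question would reopen, with an error rate of about 8% to 14% for correlations between 0.95 and 0. The conclusion is about multiplicity alone and does not endorse the effect size or the total of 6 observations.

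### The 87.4% power for 6 observations rests on a waist-circumference effect in type 2 diabetes patients and does not support the postprandial outcomes in healthy people

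*SAP*

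**What the plan says.** The SAP consists of a single Power Analysis Report. It opens with its purpose: "Statistical power analysis was applied to decide how many observations to work with". The study title it gives ends "Postprandial Glucose, Insulin and Subjective Saturation Response in Healthy Individuals".

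The effect size is taken from one reference study, of which the report says that "the independent samples t-test result applied to describe the mean difference in waist circumference was taken as a basis". The value is d = 3.429 (3.428571 in the G*Power output, Figure 2). The Reference section gives the title of that study, a trial of Salba-chia "in the treatment of overweight and obese patients with type 2 diabetes".

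From this value the report concludes that "in this study, if a total of 6 observations are studied, a test power of approximately 87.4% is reached", and then: "Since the power value we calculated is over 80%, it is statistically sufficient". Figure 2 shows a two-sided test at alpha 0.05 with "Sample size group 1 = 3" and the same number in group 2.

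**The concern.** Power belongs to a particular endpoint, population and design. Here the effect size describes a body measurement in patients with type 2 diabetes, while the study concerns acute responses to a meal in healthy people. A standardised difference is a mean difference divided by an SD, and neither part has any evident reason to be the same for post-meal glucose, insulin or satiety as for waist circumference. The report offers no reason beyond calling the reference study parallel to the planned research.

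The sufficiency conclusion is the report's stated basis for the number of observations. If the study is run at or near 6 observations, a non-significant result on glucose, insulin or satiety could be read as evidence of no effect because power was said to be 87.4%. Nothing in the report supports that reading.

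**Working it through.** **Inputs from the SAP (Figure 2):** d = 3.428571, n = 3 per group, two-sided alpha = 0.05, independent samples t-test. No mean difference or SD is printed.

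**1. Reproducing the stated figure.** Exact power from the noncentral t distribution:
- Noncentrality = d × √(n/2) = 3.428571 × √1.5 = 4.19912.
- df = 2n − 2 = 4; critical t = 2.77645.
- Power = P(|T| > 2.77645), with T noncentral t on 4 df = 0.87410.

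All four values match the printed output, so the arithmetic is not in dispute.

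**2. What the set-up can detect.** Keeping 3 versus 3 and solving for 80% power gives d = 3.07. The half-width of the 95% confidence interval for the mean difference is 2.77645 × √(1/3 + 1/3) = 2.27 SD.

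**3. Power over assumed effects.** The report gives no effect size for its own outcomes, so the d values below are assumptions that show sensitivity. They are not estimates. It also does not say whether the same people eat each product, so two paired readings are included. They assume a within-person correlation of 0.5, for which the SD of the differences equals the between-person SD and the paired effect equals d. Paired noncentrality = d × √n, with df = n − 1.

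| Assumed d | 3 vs 3 independent | 6 people paired | 3 people paired |
|---|---|---|---|
| 0.5 | 7.7% | 17% | 8% |
| 0.8 | 11.9% | 36% | 13% |
| 1.0 | 15.9% | 51% | 18% |
| 1.5 | 29.3% | 83% | 32% |
| 2.0 | 46.3% | 97% | 47% |
| Effect for 80% power | 3.07 SD | 1.43 SD of differences | 3.26 SD of differences |

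At d = 3.0, independent 3 versus 3 gives 78.3%, so the set-up approaches 80% only for effects near the borrowed one.

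The correlation matters as well. For 6 paired people at d = 1.0, power is 39%, 51%, 72% and 87% at correlations of 0.3, 0.5, 0.7 and 0.8.

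**4. Sizes for 80% power at the same assumed effects.**

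| Assumed d | Two-group total | Paired people (correlation 0.5) |
|---|---|---|
| 0.5 | 128 | 34 |
| 0.8 | 52 | 15 |
| 1.0 | 34 | 10 |
| 1.5 | 18 | 6 |
| 2.0 | 12 | 5 |

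**The case against.** The strongest reply is that the consequence is conditional. The report does not state that 6 is the planned enrolment. It says power was calculated for several sample sizes and describes what is reached if 6 are studied. The protocol is not at hand, and actual enrolment could be well above 6. This stands: what is established is an unsupported power statement, not an underpowered trial.

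A second reply is that a within-person comparison could give good power with few people. That also stands as a possibility. At d = 2.0, 6 paired people would have 97%, more than the report claims, so the direction in which a correct calculation would move the figure is not known. But the report calculates for two independent groups of 3, and a favourable paired design would not make 87.4% the right number.

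A third is that the protocol may hold effect sizes for the postprandial outcomes. It may, but the point does not rest on their absence. The report itself names the source of its effect size and applies the result to this study. A separate justification elsewhere would replace this calculation, not validate it.

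Finally, the d values and correlations used above are assumed. They are, because this document offers nothing to choose among them.

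**Conclusion.** The concern holds. The 87.4% is computed correctly from d = 3.428571, but that d describes a different endpoint in a different population, so neither the stated power nor the claim of sufficiency is supported for postprandial glucose, insulin or satiety in healthy people.

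Under the report's own set-up, 80% power exists only for differences of about 3.1 SD. Across the assumed effects of 0.5 to 2.0 SD and the three readings of the design tabulated, power runs from about 8% to 97%. That spread depends on the assumed effects and the assumed correlation of 0.5; it shows that power is unknown, not that it takes a particular low value. The mismatch itself needs no assumption, since both sides of it are printed in the report.

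The statement must be corrected whatever the enrolment. How far it affects the trial depends on an enrolment figure that this document does not give.

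**What to change.** Withdraw the statements that 6 observations give 87.4% power in this study and that this is sufficient. Redo the calculation from a mean difference and SD for the study's own postprandial endpoint in healthy people, with the test that matches the design:
- separate groups: between-person SD and an independent t-test;
- same people on each product: SD of the within-person differences and a paired test.

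If the size is already fixed, replace the power claim with the detectable difference at 80% power: about 3.1 SD with 3 per group, or, in SDs of the paired differences, about 1.43 with 6 people and 3.26 with 3. Report estimates with 95% confidence intervals, and do not cite 87.4% when interpreting a non-significant result.

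The cost is rewording and one recalculation, with no added enrolment. If the sponsor chooses to size the study for 80% power, recruitment could rise: from 12 to 128 people in total for two groups as the assumed d falls from 2.0 to 0.5, or from 5 to 34 if paired with correlation 0.5.
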